9.8.2 Emergency unblinding of treatment assignment

Most often, study drug discontinuation and knowledge of the possible treatment assignments are sufficient to treat a study participant who presents with an emergency condition. While the responsibility to break the intervention code in emergency situations resides solely with the evaluating investigator, it is recommended that the investigator contact the sponsor or its designee/study medical monitor if possible to discuss the particular situation, before breaking the blinding unless this could delay emergency treatment of the participant. Telephone contact with the medical monitor will be available 24 hours per day, 7 days per week. If a participant's intervention assignment is unblinded, the sponsor must be notified within 24 hours after breaking the blind.

The investigator will inform the participant how to contact his/her backup in cases of emergency when he/she is unavailable. The investigator will provide protocol number, study drug name if available, participant number, and instructions for contacting the sponsor (or any entity to which it has delegated responsibility for emergency

Protocol for clinical study of Brequinar

Protocol No.: 21-VIN-0372

Version No.: 2.1; Dated: 29 Dec 2021

Supersedes: 02; Date of Supersedes: 30 Sep 2021

code breaks) to the participant in case emergency unblinding is required at a time when the investigator and backup are unavailable.

An assessment will be done by the appropriate site personnel and the Study Lead after an emergency unblinding to assess whether or not study drug should be discontinued for a given participant.

In general, randomization codes will be disclosed fully only if the study is completed and the clinical database is closed.

9.9 Study Duration

Study duration will be approximately 34 days including a maximum screening period of 5 days.

9.10 Treatment

All subjects will receive standard of care (SOC) including treatment for COVID-19 signs and/or symptoms as required. Study encounters may be conducted remotely or at the study site depending on visit requirements, site facilities and subject and study team preferences.

9.11 Clinical Safety Measures

It is the responsibility of the investigator to ensure that adequate medical supervision and care is available for the study subjects during the study to ensure their utmost safety and well being.

- Demography (subject reported / measured height and weight, age, sex and race/ethnicity): At screening
- Medical history (relevant within 30 days or ongoing) / History of current illness (date of symptom onset or change in baseline co-morbidity thought to be due to COVID-19 infection): At screening
- Physical Examination (subject self-reported / examiner evaluated): At screening
- Vital signs (body temperature, respiratory rate, heart rate, SpO₂) assessment: At screening, Day 4 (± 8 hrs), Day 8 (± 8 hrs), Day 12 (± 1 day), Day 15 (± 1 day), Day 22 (± 1 day), End of study [EoS; Day 29 (± 2 day)].

Note: If subject is hospitalized, Vital signs assessment will be done on daily basis by site team during hospitalization through Day 8 then following the Vital signs visits as listed above.

- Hematology, biochemistry and urine analysis: At screening, Day 1 unless same day as Screening visit, Day 8 (± 8 hrs), Day 15 (± 1 day), End of study [EoS; Day 29 (± 2 day)].

- HCV, HbSAg, HIV Test: At screening

- Serum pregnancy test (Women of child bearing potential (WOCBP)): At screening.

- Urine pregnancy test (WOCBP): End of study [EoS; Day 29 (± 2 day)].

Note: WOCBP: A premenopausal female capable of becoming pregnant

- Rapid antigen test / SARS-CoV-2 RT-PCR Qualitative (in a clinically relevant specimen (Naso-Oro-

Protocol for clinical study of Brequinar

Protocol No.: 21-VIN-0372

Version No.: 2.1; Dated: 29 Dec 2021

Supersedes: 02; Date of Supersedes: 30 Sep 2021

Pharyngeal as appropriate)): Screening

Note: Test need not be repeated in those with possession of confirmed positive report. Date of positive report must be \leq 5 days prior to randomization.

- RT-PCR Quantitative Viral (in a clinically relevant specimen (Naso-Oro-Pharyngeal as appropriate)): Day 1 (Prior to dosing), Day 4 (\pm 8 hrs), Day 8 (\pm 8 hrs), Day 12 (\pm 1 day), Day 15 (\pm 1 day), Day 22 (\pm 1 day) and End of study [EoS; Day 29 (\pm 2 day)]
- Ordinal Scale Assessment: Screening, Day 8 (\pm 8 hrs), Day 15 (\pm 1 day), Day 22 (\pm 1 day) and End of study [EoS; Day 29 (\pm 2 day)]
- Adverse events/ Serious Adverse Events: Adverse events/ Serious Adverse Events will be recorded from the time of first study drug administration till end of study safety assessments. Other medical events not related to disease condition under study and occurring before IMP administration, but after signing the informed consent form will be recorded on the medical history/current medical conditions of case report form.
- In addition to protocol-specific laboratory tests and/or clinical examinations at scheduled time points, additional tests/clinical examination may be conducted to evaluate subject safety at any time during the study, at the discretion of the Investigator (can be done in local laboratory or nearby clinic/hospital/institution).
- Medication taken prior to first dosing: All prescription medications and over-the-counter drugs (including vitamins) taken within 30 days prior to screening must be recorded in the eCRF as Medication history.
- Concomitant medications: Medications taken from time of signing of Informed Consent form until study completion (i.e. End of study) will be captured as concomitant medications.
- Prohibited medications: Any other antiviral medications or medication with antiviral potential.

Note:

- It is recommended that general precautions need to be taken by the staff caring for COVID patients during the trial.
- In case the subject is hospitalized during the course of study, the activities specified in scheduled visits / time points will be carried out within the hospital facility.

9.12 Discontinuation/ Termination of Study

Investigator reserves the right to discontinue the study for safety reasons at any time. Ethics Committee (EC) and/or Regulatory Authority may ask to terminate the study, if there are major violations of ethical considerations or due to any serious adverse event(s). Reasons for termination of study will be provided to subjects. In case sponsor/PI decides to terminate the study, reason for the same will be notified to Central Licensing Authority within thirty working days of such termination and/or notified to EC as applicable.

Note: In case of IMP termination, ongoing subjects will continue with standard treatment based on PI's discretion.

Protocol for clinical study of Brequinar

Protocol No.: 21-VIN-0372

Version No.: 2.1; Dated: 29 Dec 2021

Supersedes: 02; Date of Supersedes: 30 Sep 2021

Discontinuation of the trial at one particular centre:

The sponsor may stop this trial at one particular centre for any of the following reasons or more:

- Serious and/or persistent non-compliance with the protocol
- False documentation in the source
- Inadequate co-operation with the sponsor, or its representatives
- Non-compliance with GCP and/or regulatory requirements
- The investigator requests discontinuation.

10.0 STUDY TREATMENT

10.1 Investigational Medicinal Product and Combination Product Dosage

1. Brequinar 50 mg capsules (used for the 50 mg and 150 mg doses)
2. Brequinar 100 mg capsules (used for the 100 mg, 150 mg and 200 mg doses)
3. Dipyridamole 75 mg tablets
4. Brequinar Placebo 50 mg and 100 mg capsules

Note:

- The subjects will take the study medication as directed on study days 1 – 5.
- Treatment assignment will be randomized, assessor-blind.
- IMP dispensing will be performed by an unblinded pharmacist.
- Study assessments will be performed by blinded Investigator or other designed blinded site personnel.
- Brequinar and brequinar placebo doses will be administered once daily.
- Dipyridamole doses will be given thrice daily.
- The 150 mg brequinar or brequinar placebo dose will be given as 1 capsule of 100 mg and 1 capsule of 50 mg; the 200 mg brequinar or brequinar placebo dose will be given as 2 capsules of brequinar or placebo 100 mg.

10.1.1 Assessment of Compliance

Compliance for dosing at home will be captured using a patient diary card.

10.2 Procurement, Storage and Accountability Procedures for Investigational Products

10.2.1 Receipt and storage of investigational products

Adequate supplies of investigational medicinal products for dosing will be distributed to the sites in bulk from the chosen depot. Investigational medicinal products will be stored per the storage condition supplied by sponsor. Certificates of analysis (COA) containing required product information will be received from sponsor.

Protocol for clinical study of Brequinar

Protocol No.: 21-VIN-0372

Version No.: 2.1; Dated: 29 Dec 2021

Supersedes: 02; Date of Supersedes: 30 Sep 2021

The hospital pharmacist will receive bulk supplies of IMP (brequinar 50 mg, brequinar 100 mg, dipyridamole 75 mg and brequinar placebo 50 mg and 100 mg) and will be unblinded to treatment. For each individual subject, the hospital pharmacist will use the IWRS to assign the randomization subject numbers. Hospital pharmacist will create an opaque, labeled zip lock bag or bottle for IMPs as assigned for individual subjects either per day or for all 5 days in the requisite packaging.

10.2.2 Accountability of investigational products

Sites will maintain accountability of IMPs received, stored, administered and returned to CRO/ destroyed at site. Only subjects enrolled in the study should be administered IMP per this protocol. Investigator/ designee supervising the dosing will be responsible for compliance to randomization schedule at site. Overall responsibility of IMP accountability at the site lies with the Investigator.

10.2.3 Handling of Unused Investigational products

Unused IMPs will be returned to the CRO or destroyed locally (per IMP plan).

10.2.4 Maintenance of Dispensing Record

A copy of site-specific dispensing record will be maintained in the Site Investigator File as well as in Central Investigator File.

10.2.5 Concomitant medication

Any allowable concomitant medication being taken by the subject should be continued on same dose during the study. Any change in the dose needs to be documented and subjects can continue in the study if the investigator deems proper. Administration of the following medications is not permitted after screening until after the end of each subject's study participation.

Prohibited Medications:

The following concomitant medications, products or procedures will not be allowed while enrolled in the study:

- Hydroxychloroquine
- Ivermectin
- Immunomodulators such as tocilizumab
- Antiviral drugs or drugs with antiviral potential including but not limited to remdesivir

The use of any of the above mentioned medications/procedure will result in withdrawal of the subject from the study.

Note: This list of drug is not exhaustive. However, any drug which is not mentioned above and having a possible on study drug efficacy and safety, should be confirmed with Medical Monitor/Medical Expert.

Protocol for clinical study of Brequinar

Protocol No.: 21-VIN-0372

Version No.: 2.1; Dated: 29 Dec 2021

Supersedes: 02; Date of Supersedes: 30 Sep 2021

Permissible Medications: Other than those prohibited.

Standard treatment [(Standard Of Care (SOC)] provided in all the arms will be per the latest updated version of CLINICAL MANAGEMENT PROTOCOL for COVID-19 (in adults) released by Government of India Ministry of Health and Family Welfare Directorate General of Health Services (EMR Division).

If drug therapy other than that specified in the protocol is required prior to or during the study period, decisions shall be taken by the investigator to continue or discontinue the subject based on the following:

- The pharmacology and pharmacokinetic of the non-study medication.
- The likelihood of a drug–drug interaction.
- The time and duration of administration of the non-study medicine.

The start and stop date of concomitant medication use during the study should be recorded in source data. All such instances will be recorded and reported in the final report with details of start date, stop date and reason for medication use.

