i. Subjects hospitalization will be based on the discretion of the Investigator. Hospitalization for the purpose of PK sample collection can be done at Investigator's discretion, in this case hospitalization may be for selected few days and may not be for entire 8 days duration. Subjects may leave the hospital after the Day 8 samples have been obtained if medically able to be discharged. In case the subject is hospitalized during the course of study, the activities specified in scheduled visits / time points will be carried out within the hospital facility.

Protocol for clinical study of Brequinmar
Protocol No.: 21-VIN-0372
Version No.: 2.1; Dated: 29 Dec 2021
Supersedes: 02; Date of Supersedes: 30 Sep 2021

- j. Sample collection for performing laboratory tests on days 1, 8, 15 and 29 will be conducted at the site or via home visit.
- k. If a study subject is discontinued from the study during an unscheduled visit, the unscheduled visit will be referred to as an Early Discontinuation Visit and all procedures scheduled for End of Study Visit will be performed.
- l. RT-PCR Quantitative Viral will be done at Day 1 (Prior to dosing), Day 4 (± 8 hrs), Day 8 (± 8 hrs), Day 12 (± 1 day), Day 15 (± 1 day), Day 22 (± 1 day) and End of study [EoS; Day 29 (± 2 day)]
- m. Day 1 unless same day as Screening visit.

Note:

- If the unscheduled visit is not an Early Discontinuation Visit (i.e., the study subject will continue to take part in the study), then the reason for unscheduled visit is to be documented and required procedures at the discretion of investigator considering the reason for visit, will be performed.

Protocol for clinical study of Brequinar
 Protocol No.: 21-VIN-0372
 Version No.: 2.1; Dated: 29 Dec 2021
 Supersedes: 02; Date of Supersedes: 30 Sep 2021

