8.3 Withdrawal Criteria

Subjects may voluntarily withdraw from the study at any time without assigning any reason thereof by withdrawing their consent. They may be considered withdrawn if they state an intention to withdraw, or fail to return for visits, or become lost to follow up for any other reason.

If premature withdrawal occurs for any reason, the investigator must determine the primary reason for a patient's premature withdrawal from the study and record this information in the CRF. For patients who are lost to follow-up (i.e., those patients whose status is unclear because they fail to appear for study visits without stating an intention to withdraw), the investigator should show "due diligence" by documenting in the source documents steps taken to contact the patient, e.g., dates of telephone calls, other means of communication even though patient is unwilling to attend further visits etc.

If study participation is discontinued, the final evaluation will be performed as completely as possible. Any comments (spontaneous or elicited) or complaints made by the patient and the reason for termination, date of stopping the study medication and the total amount of study medication must be recorded in the source documents or CRFs.

Protocol for clinical study of Brequinar

Protocol No.: 21-VIN-0372

Version No.: 2.1; Dated: 29 Dec 2021

Supersedes: 02; Date of Supersedes: 30 Sep 2021

Criteria for a withdrawal of patients from clinical study:

The subject may be withdrawn from the trial at the discretion of the investigator or the sponsor, if judged non-compliant with trial procedures or due to safety concern.

A subject must in addition be withdrawn from treatment with IMP if the following applies:

- AE requiring permanent discontinuation of study drug.
- The subject suffers from significant intercurrent illness or undergoes surgery requiring study discontinuation during the course of the study.
- Any subject who requires the use of an unacceptable concomitant medicine.
- If the Investigator believes it is not in the subject's best interest to continue.
- The subject wishes to withdraw his/her consent.
- Any other justifiable reason, which should be adequately documented.
- Any subject whose condition worsens, requiring treatment with immunomodulators including but not limited to tocilizumab and / or antiviral drugs including but not limited to remdesivir as per the best judgement of the Investigator.

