- Non-compliance: The participant may be withdrawn from the trial at the discretion of the Investigator if it is judged that participant is non-compliant to study assessment and schedule leading to safety concerns.
- Positive pregnancy test: A female participant with a positive pregnancy test will be withdrawn from the trial.

The sponsor or its representative may be contacted for clarification as required on a case-by case basis.

Handling of Withdrawals:

In the case of premature discontinuation of study subject, the investigator should schedule a study discontinuation visit to complete all assessment according to End of Study / Early Termination visit requirements. All reasons for ending participation must be recorded in the source documents or in the CRF.

If the subject discontinues because of an adverse event (serious or non-serious), the investigator must follow up patient's recovery until resolution or stabilization of AEs or up to 30 days after administration of last dose of IMP, whichever is earlier.

This visit should be documented in the appropriate section of the Case Report Form (CRF). The investigator will record the reason for study discontinuation, provide or arrange for appropriate follow-up for such subjects, and document the course of the subject's condition. In addition, the investigator will report the subject's withdrawal to the responsible study monitor immediately.

Subjects withdrawn from investigational product treatment will be treated as routine subjects. The investigator will discuss the appropriate therapy with each subject who withdraws early from this study. Determination of the appropriate follow-on therapy will be left to the discretion of the investigator and investigator could treat such subjects as per his/her routine practice.

Protocol for clinical study of Brequinar
 Protocol No.: 21-VIN-0372
 Version No.: 2.1; Dated: 29 Dec 2021
 Supersedes: 02; Date of Supersedes: 30 Sep 2021

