12.9 Handling and Reporting of Adverse Events

An adverse event is any untoward medical occurrence (including a symptom or disease or an abnormal laboratory finding) during treatment with an investigational drug or a pharmaceutical product in a subject that does not necessarily have a relationship with the treatment being given.

*Abnormalities based on laboratory parameters, vital signs, and 12-Lead ECG will be called AE, if they are associated with at least one of the following:

- Interruption or stoppage of the study medication
- Associated with signs or symptoms
- Requiring treatment
- Considered clinically significant by the investigator

Safety Criteria:

An independent, unblinded study physician (from CRO) will assess each cohort for safety. A cohort will be declared safe as soon as all results are available for the Day 15 visit if the following conditions are met:

- No toxic deaths (deaths judged by the investigator to be related to either study drug);
- Not more than 1 toxic SAE (SAEs judged by the investigator to be related to either study drug);
- No Grade 3 or higher toxicities (including laboratory AEs as per CTCAE version 5.0 or higher) (AEs judged by the investigator to be related to either study drug);
- <4 subjects with any grade toxicity (AEs judged by the investigator to be related to either study drug).

In addition to the cohort-level safety, the independent study physician (from CRO) will determine if any subjects meet Individual Stopping Criteria:

- Subjects who develop a Grade 3 toxicity that is assessed by the investigator to be related to the study drug are to be permanently discontinued from study treatment but will continue in the study for safety assessments.
- Subjects who develop a Grade 4 toxicity, regardless of relatedness to study drug, are to be permanently discontinued from study treatment but will continue in the study for safety assessments.

In addition to the individual subject-level safety, the independent study physician (from CRO) will determine if a cohort meets Cohort-level Stopping Criteria prior to completing the 16 subjects, in which case no additional subjects will be enrolled into that cohort and no higher brequinar doses will be assessed:

Protocol for clinical study of Brequinar

Protocol No.: 21-VIN-0372

Version No.: 2.1; Dated: 29 Dec 2021

Supersedes: 02; Date of Supersedes: 30 Sep 2021

- ≥ 3 brequinar-treated or combination-treated subjects meet the individual stopping criteria.

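### Use of a listed rescue drug ends study participation under section 10.2.5, and nothing keeps these subjects in scheduled visits, so outcome-related viral-load and symptom data through Day 29 can be lost

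*Combined protocol and SAP*

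**What the plan says.** All references are to protocol Version 2.1. The text of the separate SAP is not among the documents.

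- **Section 10.2.5** bars hydroxychloroquine, ivermectin, immunomodulators and antivirals from screening to the end of participation. The consequence of use is: "The use of any of the above mentioned medications/procedure will result in withdrawal of the subject from the study".
- **Section 8.3** has a list introduced by "A subject must in addition be withdrawn from treatment with IMP if the following applies". It includes "Any subject who requires the use of an unacceptable concomitant medicine" and "Any subject whose condition worsens, requiring treatment with immunomodulators including but not limited to tocilizumab and / or antiviral drugs". The heading above the list, however, speaks of withdrawal from the clinical study.
- **Section 8.3, on handling withdrawals**, provides one discontinuation visit with End of Study assessments. It also says "Subjects withdrawn from investigational product treatment will be treated as routine subjects". It asks the investigator to arrange suitable follow-up and document the subject's course, but names no swab or form.
- **Section 3.2, note k**, says that at an early discontinuation visit "all procedures scheduled for End of Study Visit will be performed". Section 9.4 agrees, and lets the investigator discontinue a worsening subject as a treatment failure.
- **Section 12.9** treats toxicity differently. Subjects with a related Grade 3 or any Grade 4 toxicity are "permanently discontinued from study treatment but will continue in the study for safety assessments".
- **Section 10.1** limits dosing: "The subjects will take the study medication as directed on study days" 1 to 5.
- **Sections 15.1, 15.3 and 15.4** define an ITT set of all randomised subjects, plan ANCOVA of viral load at six visits through Day 29 and Kaplan-Meier analysis of time to symptom improvement, and leave missing data to the SAP.

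**The concern.** Stopping study drug and stopping follow-up are separate decisions. The protocol separates them for toxicity but not for rescue medication. A subject who worsens and is given remdesivir or tocilizumab leaves the study under 10.2.5, and the remaining scheduled measurements are not taken.

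Section 8.3 itself describes immunomodulator and antiviral use as a response to worsening, so for those two classes the missing values are not a random sample. The same cannot be said of hydroxychloroquine or ivermectin, which 8.3 does not name in that context.

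At stake are the secondary viral-load comparison, which section 11.0 makes the main measure of efficacy, and the time to symptom improvement. An ITT set that includes everyone randomised is of limited use if subjects who needed rescue have no late data.

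**Working it through.** The protocol gives no figure for rescue or dropout, so there is none to reproduce. The check has four steps.

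**1. Which rule operates, and when.** Dosing ends on Day 5. From Day 6 a rule that withdraws a subject from study drug has nothing left to stop, so 10.2.5 is the rule with effect. Three texts might have kept the subject in visits, and none does:
- The stay-in-study rule in 12.9 covers toxicity only.
- The provision in 9.2 for doing scheduled activities in hospital applies to subjects still in the study.
- The investigator-discretion clause in 10.2.5 concerns therapy other than that specified in the protocol.

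**2. What one withdrawal loses.** Post-baseline swabs fall on Days 4, 8, 12, 15, 22 and 29; symptom forms on Days 1–8, 12, 15, 22 and 29; post-baseline routine laboratory tests on Days 8, 15 and 29 (sections 9.2 and 9.11).

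| Withdrawn on | Swabs lost | Symptom forms lost | Laboratory visits lost |
|---|---|---|---|
| Day 6 | 5 (8, 12, 15, 22, 29) | 6 (7, 8, 12, 15, 22, 29) | 3 (8, 15, 29) |
| Day 10 | 4 (12, 15, 22, 29) | 4 (12, 15, 22, 29) | 2 (15, 29) |

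One off-schedule set from the discontinuation visit is gained in return. Section 5.4 reports that in the earlier outpatient study the numerical (non-significant) viral-load difference began at Day 12. Withdrawal on Day 10 removes every scheduled swab in that window.

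**3. Weight of one subject (1/n).**
- Within a cohort: brequinar alone or placebo 1/4 = 25%; combination 1/8 = 12.5%.
- At the expanded dose: brequinar alone 1/(4+16) = 5%; combination 1/(8+32) = 2.5%.
- Pooled over cohorts: placebo 1/16 = 6.25%; combination with expansion 1/(32+32) = 1.6%.

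**4. How many subjects.** The nearest proxy is in 5.4: 1 of 115 outpatients was admitted for COVID-19 pneumonia.
- Rate: 1/115 = 0.87%, exact 95% CI 0.02% to 4.75%.
- Expected in Part 1: 64 × 0.0087 = 0.56 (0.01 to 3.0 over the CI).
- Expected with the expansion: 112 × 0.0087 = 0.97 (0.02 to 5.3).
- Chance of at least one, 1 − (1 − 1/115)^N: 43% for N = 64, 62% for N = 112.
- Chance of at least one in a given arm of 4: 1 − (114/115)^4 = 3.4%.

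Admission is not the same as use of a listed drug, and this trial also enrols moderate disease, so the true rate could be higher. In the hospitalised study at least 2 of 15 brequinar subjects received remdesivir, but they were sicker and do not supply a rate for this trial.

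**The case against.** The case for leaving the text alone has real content.

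- **Sections 10.2.5 and 8.3 may not conflict.** A reader might infer two contradictory rules. The 8.3 list sits under a heading on leaving the clinical study, its lead-in adds to that, and it includes withdrawal of consent. Read so, 8.3 agrees with 10.2.5. This stands: the text is ambiguous, not clearly contradictory. The agreeing reading does not save the data, since it makes study withdrawal the sole instruction.
- **The direction of bias is not known.** A reader might infer that the arm with more rescue is flattered. That depends on the missing-data method. Carrying forward the discontinuation swab, or scoring rescue as failure, could work the other way. This stands.
- **A SAP could do part of the job.** Counting rescue for worsening as not improved needs only its date and reason, and 10.2.5 already requires start date, stop date and reason for concomitant medication. This stands for time to symptom improvement. It does not help viral load, where a swab that was never taken cannot be analysed.
- **Retained swabs may be taken under an antiviral.** True, and a cost of the fix. Such samples can be flagged by date; absent ones cannot.
- **Other endpoints may be little affected.** Someone who worsens enough to need these drugs may already count as an event for admission, attended visits or oxygen. This is plausible, and the point is confined to viral load and symptoms.
- **The stakes are modest.** Efficacy testing is exploratory, the trial is unpowered, and few subjects are likely to be involved. This limits the weight of the point without removing it.

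**Conclusion.** The concern holds in a limited form. As written, 10.2.5 ends participation on use of a listed drug, 8.3 does not clearly say otherwise, and only one discontinuation visit is secured. For immunomodulators and antivirals the resulting loss through Day 29 is related to outcome and can bias two exploratory secondary comparisons, in a direction the documents do not settle. The likely number is small: about 0.6 subjects in 64 or 1.0 in 112, if the 1/115 admission rate is a fair stand-in for rescue.

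Two stronger readings are not supported. A reader might infer that the primary safety endpoint is compromised. The effect there is small, because toxicity stops remain in the study under 12.9 and section 12.11 follows adverse events whether or not the subject is still participating; what is lost is the later routine laboratory visits. A reader might also take the 25% weight as the expected impact. It applies only if the event falls in an arm of 4, which has about a 3.4% chance for a given arm on the same proxy, and the weight is far smaller in pooled or expanded arms.

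The change is worth making because the stated rule itself causes the loss and the visits that would prevent it are already scheduled.

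**What to change.** 1. Amend 10.2.5 and 8.3 so that use of a listed drug stops any remaining study drug, and the subject completes scheduled assessments through Day 29 unless consent is withdrawn.
2. Keep the investigator's safety discretion in 9.4, but add that stopping treatment for worsening does not by itself end scheduled follow-up.
3. In the SAP, if not already there, use all collected data in the ITT set, with a supportive analysis that counts rescue for worsening as not improved through Day 29.

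No new recording is needed, since 10.2.5 already asks for dates and reason. A minor tidy-up in the same amendment would be one prohibition window: exclusion 5 bars remdesivir and ivermectin through Day 8, 10.2.5 bars them to the end of participation, and 9.11 gives no limit for antivirals. A site can satisfy all three by following 10.2.5, so nothing turns on this, and the choice of window is clinical.

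The cost is a few sentences in the protocol and one SAP paragraph, with no added visits. The amendment needs ethics and regulatory approval under section 16.0, and some late viral loads will be measured under rescue therapy.
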